7.3. Vital Signs, Weight and BMI

Descriptive statistics for values and changes from baseline at each scheduled time-point during the double-blind and follow up phases will be presented for Systolic Blood Pressure (mmHg), Diastolic Blood Pressure (mmHg), Pulse Rate (beats per minute), Weight (kg), and BMI. In addition, descriptive statistics of pulse rate and blood pressure (systolic and diastolic) values and changes from predose will be provided for each timepoint.

The proportion of subjects who have a treatment-emergent abnormality, as defined in Table 5 below, will be presented for the double-blind phase. The double-blind baseline will be used to determine abnormal values. A listing of subjects meeting any of the criteria will also be provided for the double-blind phase.

Table 5: Treatment-Emergent Abnormality Categories for Vital Signs			
Vital Parameter	Post-baseline value outside of normal limit if:		
	Abnormally low	Abnormally high	
Pulse (bpm)	A decrease from baseline of	An increase from baseline of	
	≥ 15 to a value ≤ 50	≥ 15 to a value ≥ 100	
Systolic BP	A decrease from baseline of	An increase from baseline of	
(mmHg)	≥ 20 to a value ≤ 90	≥ 20 to a value ≥ 180	
Diastolic BP	A decrease from baseline of	An increase from baseline of	
(mmHg)	≥ 15 to a value ≤ 50	≥ 15 to a value ≥ 105	

BP = blood pressure

7.4. Other Safety Parameters

7.4.1. Columbia Suicide Severity Rating Scale

The C-SSRS is a low-burden measure of the spectrum of suicidal ideation and behavior. It is a semi structured clinician-administered questionnaire designed to solicit the occurrence, severity, and frequency of suicide-related ideation and behaviors during the assessment period.

As noted in the August 2012 draft guidance titled "Suicidal Ideation and Behavior: Prospective Assessment of Occurrence in Clinical Trials",³ the FDA has outlined 11 categories of interest, obtained by the C-SSRS instrument. Some data collected on the C-

SSRS are not used for analysis, but are used for individual clinical management and safety monitoring (e.g., suicidal behavior lethality and suicidal ideation intensity). These data are not included in the proposed analysis tables.

The summaries of the C-SSRS outcomes will be based on the safety analysis set subjects who have at least 1 post-baseline C-SSRS measurement and a pre-treatment C-SSRS assessment (lifetime assessment at screening). The C-SSRS outcomes will be summarized in double-blind phase.

The following outcomes are C-SSRS categories and have binary responses (yes/no). The categories have been re-ordered from the actual scale to facilitate the definitions of the composite and comparative endpoints, and to enable clarity in the presentation of the results.

Categories

Category 1 – Wish to be Dead

Category 2 - Non-specific Active Suicidal Thoughts

Category 3 - Active Suicidal Ideation with Any Methods (Not Plan) without Intent to Act

Category 4 - Active Suicidal Ideation with Some Intent to Act, without Specific Plan

Category 5 - Active Suicidal Ideation with Specific Plan and Intent

Category 6 - Preparatory Acts or Behavior

Category 7 – Aborted Attempt

Category 8 – Interrupted Attempt

Category 9 – Actual Attempt (non-fatal)

Category 10 - Completed Suicide

Self-injurious behavior without suicidal intent is also a C-SSRS outcome (although not suicide-related) and has a binary response (yes/no).

The following outcome is a numerical score derived from the C-SSRS categories. The score is created at each assessment for each patient and is used for determining treatment emergence.

• Suicidal Ideation Score: The maximum suicidal ideation category (1-5 on the C-SSRS) present at the assessment. Assign a score of 0 if no ideation is present.

Composite endpoints based on the above categories are defined below.

• Suicidal ideation: A "yes" answer at any time during treatment to any one of the five suicidal ideation questions (Categories 1-5) on the C-SSRS.

• Suicidal behavior: A "yes" answer at any time during treatment to any one of the five suicidal behavior questions (Categories 6-10) on the C-SSRS.

Comparative endpoints of interest are defined below. "Treatment emergence" is used for outcomes that include events that first emerge or worsen. "Emergence" is used for outcomes that include events that first emerge.

• **Treatment-emergent suicidal ideation** compared to all prior history:

An increase in the maximum suicidal ideation score during treatment from the maximum suicidal ideation score prior to treatment.

• **Emergence of serious suicidal ideation** compared to all prior history:

An increase in the maximum suicidal ideation score to 4 or 5 during treatment from no suicidal ideation (scores of 0) prior to treatment.

• **Treatment-emergent serious suicidal ideation** compared to all prior history:

An increase in the maximum suicidal ideation score to 4 or 5 on the C-SSRS during treatment from not having serious suicidal ideation (scores of 0-3) prior to treatment.

• **Emergence of suicidal behavior** compared to all prior history:

The occurrence of suicidal behavior (any of the Categories 6-10) during treatment from not having suicidal behavior (any Categories 6-10) prior to treatment.

A summary of pre-treatment suicidal ideation and suicidal behavior will be presented in terms of percent of subjects with lifetime suicidal ideation, lifetime suicidal behavior, lifetime self-injurious behavior without suicidal intent.

Improvement in suicidal ideation compared to all prior history:

The occurrence of a suicidal ideation score (any of the Categories 1-5) during treatment lower than the suicidal ideation score (Categories 1-5) prior to treatment. Subjects with a

score of 0 prior to treatment (no ideation is present) will not be classified as having improved even if they did not experience any ideation during the study, ie, suicidal ideation score remains 0 post treatment.

The number and percent of subjects with treatment-emergent suicidal ideation, treatment emergent serious suicidal ideation, emergence of serious suicidal ideation and improvement in suicidal ideation and emergence of suicidal behavior in the double-blind phase will be summarized by treatment group in frequency and shift tables.

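### Every C-SSRS harm outcome with a specified by-arm count is judged against lifetime history, and the on-treatment composites that the SAP defines are left off the list

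*SAP*

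**What the plan says.** All of this is in SAP section 7.4.1 unless stated otherwise.

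- **Reference.** Subjects enter the summaries if they have a post-baseline C-SSRS and "a pre-treatment C-SSRS assessment (lifetime assessment at screening"). The comparative endpoints are each headed as comparisons with the subject's entire prior history.
- **Treatment-emergent ideation:** "An increase in the maximum suicidal ideation score during treatment from the maximum suicidal ideation score prior to treatment".
- **Emergence of serious ideation:** "An increase in the maximum suicidal ideation score to 4 or 5 during treatment from no suicidal ideation (scores of 0) prior to treatment".
- **Serious ideation, treatment-emergent:** a rise to 4 or 5 "during treatment from not having serious suicidal ideation (scores of 0-3) prior to treatment".
- **Emergence of behavior:** "The occurrence of suicidal behavior (any of the Categories 6-10) during treatment from not having suicidal behavior (any Categories 6-10) prior to treatment".
- **Composites with no history condition.** Ideation is "A 'yes' answer at any time during treatment to any one of the five suicidal ideation questions (Categories 1-5) on the C-SSRS". Behavior is "A 'yes' answer at any time during treatment to any one of the five suicidal behavior questions (Categories 6-10) on the C-SSRS".
- **What is tabulated.** The sentence that fixes the by-arm statistics begins "The number and percent of subjects with treatment-emergent suicidal ideation, treatment emergent serious suicidal ideation, emergence of serious suicidal ideation". It goes on to improvement in ideation and emergence of behavior, in frequency and shift tables. Neither composite is in it.
- **Baseline.** Section 2.4 defines baseline as the last value before the first dose, and Table 1 gives the C-SSRS a Day 1 predose baseline. None of the four harm outcomes is referenced to it.

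**The concern.** A trial in major depression needs a plain count, by arm, of subjects who had suicidal behavior or serious ideation while on study drug. The listed outcomes answer a narrower question: who went beyond anything in their lifetime record. A subject with an earlier attempt who attempts again on treatment falls outside every listed harm. So does a subject with past serious ideation who was free of it on Day 1 and returns to the same level. Both stay in the denominator, because the C-SSRS population is not restricted to subjects who could still show emergence.

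The improvement outcome is in the same list and uses the same lifetime reference, so a subject who has worsened since the first dose can be tabulated as improved.

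The SAP treats other safety data differently. Section 7.3 judges vital-sign abnormalities against the double-blind baseline. Section 7.1 counts a pre-existing adverse event as treatment-emergent if its severity increases after treatment starts.

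**Working it through.** The SAP states no figure on this point, so the check applies its definitions to every combination of lifetime and on-treatment status.

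**Behavior (Categories 6-10)**

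| Lifetime | On treatment | Emergence of behavior (listed) | Any behavior (defined, not listed) |
|---|---|---|---|
| no | no | no | no |
| no | yes | counted | counted |
| yes | no | no | no |
| yes | yes | **not counted** | counted |

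**Serious ideation on treatment (score 4 or 5)**

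| Lifetime maximum | On treatment | Treatment-emergent ideation | Emergence of serious | Treatment-emergent serious |
|---|---|---|---|---|
| 0 | 4 or 5 | yes | yes | yes |
| 1, 2 or 3 | 4 or 5 | yes | no | yes |
| 4 | 4 | no | no | no |
| 4 | 5 | yes | no | no |
| 5 | 4 | no | no | no |
| 5 | 5 | no | no | no |

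There are 6 × 2 = 12 combinations. All 4 × 2 = 8 with a lifetime maximum of 0-3 are counted. Of the other four, 4-to-5 is counted, as treatment-emergent ideation only. The remaining three (4-to-4, 5-to-4, 5-to-5) enter no listed harm.

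Both serious-ideation outcomes imply a score above the lifetime maximum. So an ideation case is counted somewhere if and only if the on-treatment maximum exceeds the lifetime maximum. With a lifetime score of 5, no ideation harm is possible.

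**Improvement.** Take lifetime 5, Day 1 score 0, on-treatment 4. The score 4 is below the prior score of 5, and the exclusion for a prior score of 0 does not apply because lifetime history is 5. The subject meets the definition of improvement and appears in no harm row.

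**Size, under assumptions.** Let h be the proportion of subjects with lifetime behavior, and r their on-treatment risk relative to the others. The share of subjects with on-treatment behavior who fall outside the listed harm is

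s = hr / (hr + 1 − h).

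| h | r = 1 | r = 3 | r = 5 |
|---|---|---|---|
| 0.1 | 10% | 0.3/1.2 = 25% | 0.5/1.4 = 36% |
| 0.2 | 20% | 0.6/1.4 = 43% | 1.0/1.8 = 56% |
| 0.3 | 30% | 0.9/1.6 = 56% | 1.5/2.2 = 68% |
| 0.4 | 40% | 1.2/1.8 = 67% | 2.0/2.6 = 77% |

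The SAP gives neither h nor r. For ideation of 4-5 the same expression, with h the proportion with lifetime 4-5, is an upper limit, because 4-to-5 is counted. If s is equal in both arms, the counted risk difference is (1 − s) times the true one and the risk ratio is unchanged.

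**After the fix.** The behavior composite counts yes-to-yes. The ideation composite counts 4-to-4, 5-to-4 and 5-to-5 as ideation. Counting them as serious ideation needs a further row, on-treatment score 4-5, which the SAP does not define. The lifetime 5, Day 1 score 0, on-treatment 4 subject counts as an increase from Day 1 and as a rise to 4-5 from 0-3. Relative to Day 1 that subject no longer counts as improved, since the SAP excludes a prior score of 0.

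**The case against.** The lifetime reference is stated openly, and exceeding a prior maximum is a legitimate form of worsening. The tabulation sentence can be read as fixing the format for the comparative endpoints only. Section 7.4.1 also says in general terms that C-SSRS outcomes will be summarized for the double-blind phase, and it calls the yes/no categories outcomes. A shift table from lifetime history could show the yes-to-yes and 4-5-to-4-5 cells. Behavior reported as an adverse event or serious adverse event appears by arm under section 7.1 whatever the history. Section 4.2.2 summarizes individual HDRS₁₇ items, including the suicide item, as change from baseline.

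Much of this stands as mitigation, and it rules out three stronger readings that a reader might infer:

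- *All serious ideation in subjects with earlier serious ideation goes uncounted.* It does not: a 4-to-5 rise is counted.
- *These subjects disappear from the report.* The SAP does not support that, because the outputs above may show some of them.
- *The comparison is biased toward no signal.* The rule is the same in both randomized arms. It costs sensitivity and shrinks the absolute difference, but does not by itself favor one arm. What falls outside the listed harms is recurrence, and first occurrences are counted.

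The mitigation does not close the gap. The general statement names no table or statistic, and the shift-table layout and reference are not given. Adverse event reporting is not the prospective C-SSRS analysis, and the HDRS₁₇ item summaries belong to the efficacy analyses. None of it addresses the improvement outcome.

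**Conclusion.** The point holds within these limits. The only sentence that fixes a by-arm number and percent for C-SSRS harms lists four outcomes, all relative to lifetime history. It omits both on-treatment composites defined in the same section. Recurrent behavior, and serious ideation in the 4-to-4, 5-to-4 and 5-to-5 combinations, therefore have no specified by-arm count. A subject who has worsened since Day 1 can be tabulated as improved. These conclusions follow from the definitions and need no assumption.

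The size cannot be calculated from the SAP. The 10% to 77% range for behavior rests wholly on assumed h (0.1 to 0.4) and r (1 to 5). It describes the listed harm alone, before anything recovered from other outputs. The shrinkage of the risk difference by s further assumes the same share in both arms. The change is worth making because suicidality is a central safety question in this population and the correction is small.

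**What to change.** In SAP section 7.4.1, extend the sentence listing what is tabulated by treatment group to include:

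1. any suicidal behavior and any suicidal ideation during treatment, as already defined, regardless of history;
2. on-treatment ideation score of 4 or 5, regardless of history;
3. increase in maximum ideation score, and increase to 4-5 from 0-3, each relative to the Day 1 predose C-SSRS.

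Also show improvement relative to Day 1, and state which pre-treatment assessment the shift tables start from. Keep the lifetime-based outcomes alongside.

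The cost is SAP wording and a few more table rows. Table 1 already provides for the Day 1 and post-baseline C-SSRS, so no new data are needed.
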